Aerobic Training to Improve Energy Utilization and Antioxidant Capacity in Stroke NCT02043574 Version 4/16/2019

Principal Investigator: [name] Sponsor or funding source: Department of Veterans Affairs

Fifteen to 30% of stroke survivors are disabled permanently, resulting in functional dependence and a sedentary lifestyle following stroke. Hemiparetic gait, a common disability after stroke, elevates the energy cost of ambulatory activity by 1.5-2 fold, but it is currently unknown how chronic stroke affects total daily energy expenditure and dietary intake. Altered energy balance following a stroke (expenditure ≠ intake) may result in impaired substrate utilization (fat versus carbohydrate oxidation), the production of oxidative stress and ultimately decreased cardiovascular and muscular endurance leading to increased fatigue.

This project will compare the effects of chronic treadmill training plus "heart healthy" nutrition modification versus whole body stretching plus nutrition on energy balance (dietary intake, resting metabolic rate, and exercise and non-exercise energy expenditure) and substrate utilization (measured during an acute exercise bout) in older chronic stroke survivors. Furthermore, to examine mechanisms of change, we measured changes in markers of oxidative stress before and after the interventions.

Aim 1: To assess the effects of six months of TM+N versus ST+N on total daily energy expenditure (primary outcome) and substrate oxidation in chronic stroke survivors.

Aim 2: To examine the effects of six months of TM+N versus ST+N on systemic oxidative stress in chronic stroke survivors.

Experimental Design

Overview: This project is designed to determine whether treadmill training plus nutrition (TM+N) versus stretching plus nutrition (ST+N) (control) will 1) improve energy expenditure and substrate oxidation and 2) reduce systemic oxidative stress. We will study men and women with chronic stroke and stable neurological deficits.

Eligibility criteria include:

- Age >20 years
- BMI 20-50 kg/m²
- History of stroke at least 6 months prior
- Adequate language and neurocognitive function to safely participate in informed consent, and exercise testing and training
- Completion of all conventional inpatient and outpatient physical therapy
- Capable of walking 3 consecutive minutes on a treadmill at 0.1 MPH with handrail support
- Under the care of a primary care medical provider
- Written consent from their doctor that it is safe for them to participant in physical activity.

Exclusions: Exclusion criteria include:

• Medical History: a) recent hospitalization (less than 3 months prior to study entry) for severe medical disease, b) peripheral arterial disease with vascular claudication, c) orthopedic or chronic pain condition restricting exercise, d) pulmonary or renal failure, e) active cancer, f) untreated poorly controlled hypertension measured on at least 2 occasions (greater than 160/100) g) type I diabetes mellitus, untreated and / or poorly controlled diabetes with fasting blood glucose of greater than 200 and HbA1c greater than 10.0, i) currently pregnant

• Neurological history: a) dementia by clinical evaluation b) severe receptive or global aphasia which confounds testing and training, operationally defined as unable to follow 2 point commands, c) neurologic disorder restricting exercise, such as Parkinson's Syndrome, d) untreated major depression

• Increased alcohol consumption defined as greater than 2 oz. liquor or 2 times 4 oz. glasses of wine or 2 x 12 oz. cans of beer per day

- Treatment with hormone replacement therapy
- Cardiac history of: a) unstable angina, b) recent (less than 3 months prior to study entry) myocardial infarction, congestive heart failure (NYHA category II-IV); c) hemodynamically significant valvular dysfunction

Subjects will be randomized to TM+N or ST+N (1:1 allocation). Groups will be matched for sex and race. All subjects will be studied at baseline and after 6 months of TM+N or ST+N. This design will allow us to determine total daily energy expenditure, nutritional intake, and substrate oxidation following six months of TM+N and ST+N in older stroke survivors. Further, the design will enable us to determine the effects of TM+N and ST+N on systemic oxidative stress.

Metabolic Test by Phase

The experimental design of this study involves 7 phases, completed over 9-10 months (**Table 1**). *Phase* 1 involves screening and enrollment. *Phase* 2 involves baseline testing. Volunteers then will be randomly assigned to TM+N or ST+N (control) (*Phase 3*). *Phase 4* consists of 2 weeks of weight and dietary stabilization prior to baseline research testing. *Phase 5* consists of 2 week testing (post heart healthy). *Phase 6* consists of 6 months of TM+N or ST+N. After the intervention, subjects will undergo final research testing (*Phase 7*).

Subject Screening and Enrollment (Phase 1)

a) Screening Visits: Eligible volunteers will have the study explained and provide informed consent according to the guidelines of the local Institutional Review Board for Human Research. A fasting blood profile for lipids, liver, renal and hematological function will be drawn. A 12-lead resting electrocardiogram (EKG) will be obtained and a medical history and physical examination performed. Height and weight will be measured using a standard physician's scale. Seated blood pressures will be measured in duplicate. Information on demographics and family medical history will be recorded. Subjects will complete the Mini Mental State Exam (MMSE) (60) and Center for Epidemiologic Studies Depression Scale (CES-D) questionnaires. Volunteers also will have a screening VO₂peak treadmill test as described below.

Table 1: Research Design		
	Time Duration	Research Activity
Phase 1	3 weeks	Screening & Enrollment
Phase 2	1 week	Baseline Testing
Phase 3	1 day	Randomization
Phase 4	2 weeks	Weight & Dietary Stabilization
Phase 5	1-2 months	Metabolic Pre Testing
Phase 6	6 months	TM+N or ST+N
Phase 7	1-2 months	Metabolic Post Testing

Baseline Testing (Phase 2): During this phase, subject will undergo a submaximal treadmill test, blood draw, and resting metabolic rate (RMR), as described below.

Randomization (Phase 3): Subjects are randomly assigned to either progressive 6 month treadmill aerobic exercise training 3 times per week plus nutritional modification or the reference control of education and stretch 2 times per week for 6 months plus nutritional modification.

Weight and Dietary Stabilization (Phase 4): Subjects will meet with a Registered Dietitian 2-3 times weekly for 2 weeks to learn "heart healthy" dietary patterns and ensure weight stabilization before metabolic testing. Details of the diet are described below. Prior to metabolic testing, subjects are asked to remain weight stable.

Metabolic Testing (Phase 5): This testing phase will occur over a period of 1-2 months for each individual. A VO₂peak treadmill test, body composition (anthropometrics, DXA, CT) tests, questionnaire completion, and functional and strength measures will occur during this phase. Subjects will be weight stabilized throughout the metabolic testing.

Treadmill Training plus Nutritional Modification versus Stretch Control plus Nutritional Modification (Phase 6):

Treadmill Training

Training programs will be individualized based on each participant's gait capacity and defined by peak heart rate (HR max) achieved during a baseline treadmill test. Training will be gradually progressed to a target of 50 minutes of exercise at 75-85% of HRR as tolerated by the subject. To assess treatment fidelity, staff will monitor progression weekly. A program of home walking equivalent in intensity and duration (3 days/week) to the current treadmill intensity and duration (3 days/week) will be recommended. Safety during treadmill training will be assured with a parachute style safety harnesses in non-weight bearing mode to support truncal balance, if necessary, to reduce the risk of fall. Participants may also use light handrail support. After stroke, the paretic arm is often less effective for support.

Stretch Controls:

Stretch controls will be enrolled in supervised stretching program for 2 days/week for 1 hour sessions. The stretch program will focus on basic mobility skills, including balance, sit-to-stand, weight shifting, and leg strength. Exercises will be performed in standing, seated, and lying positions. The stretching group will serve as an attention control.

Nutritional Modification: All participants will undergo up to 2 weeks nutritional modification counseling in Phase 4. These nutritional sessions will instruct participants how to consume an isocaloric, "heart healthy" diet with adequate protein (<30% of calories as fat, <10% as saturated fat, <2,400 mg sodium, 25 g/d of fiber, and 1.0-1.2 g/kg/d of lean protein) with a registered dietitian (RD). The RD will collect 24-hour or 3-5 day food records during the counseling session to ensure understanding of the dietary prescription. Additionally, compliance will be assessed throughout the remainder of the study in Phases 5-7 by periodic food records as deemed necessary on an individual basis. Weight will be monitored throughout the study to ensure weight stability. Additional dietary instruction will be provided to adjust caloric intake if weight fluctuates $\pm 2\%$.

Post Intervention Metabolic Testing (Phase 7): Body weight must be stable \pm 0.25 kg over the two week period prior to post-testing. Subjects will repeat tests outlined in Phase 5. Metabolic assessments will be performed ~36 hrs after the last bout of exercise or stretching and participants will continue to train or stretch during the post-testing period, respectively.

Study Procedures

1. Screening and Baseline Evaluations: Questionnaires to screen for depression and dementia will be administered to determine eligibility. Credentialed study staff evaluate all participants to determine whether their basic rehabilitation needs have been addressed before study entry. Participants will undergo standard medical and neurological examinations to establish medical eligibility and to characterize neurological deficits. Structured neurological evaluations may include range of motion tests, manual motor testing, and sensory examinations.

2. Blood and Urine Analyses: We will measure heart disease risk factors, CBC, comprehensive metabolic panel, lipid profile, glucose, insulin, free fatty acids, cytokines, oxidative stress, antioxidant capacity, triglycerides, lipoprotein lipids, leptin, and adiponectin. A urine pregnancy test is performed prior to the DXA and CT scans, if the participant is a woman with child bearing potential.

3. Mobility Function and Motor Control:

These tests will be administered in Phase 5 and Phase 7.

30 meter walks: Self-selected and fastest-comfortable floor walking velocity will be determined from 30 meter walks with subjects using the same assistive device and/or orthosis as normally used to "walk across the room at home." For the 30 meter walks and all walking tests described below, staff will walk beside and spot subjects to minimize risk of falls. Walks will be initiated from standing, with completion across an end line 2 meters beyond the 30 meter point, to avoid confounding from end of walk slow down. Subjects will be timed during both the self-selected and fastest comfortable paces.

6 min walk: Subjects will use the same assistive device and/or orthoses typically used and will be instructed to cover as much distance as they can in six minutes over a flat walking surface.

Timed Up and Go (TUG): Subjects are observed and timed while they rise from a chair, walk 3 meters, turn around, walk back, and sit down. A series of 3 TUGs will be performed to assess economy of this simulated ADL. An assistive device and/or orthoses may be used.

4. Treadmill Tests:

Peak: Treadmill tests will start at a self-selected pace, and will be advanced by adequate increments according to tolerance, perceived exertion, and medically credentialed clinician rating of gait stability. This clinically supervised test will determine treadmill gait safety, functional eligibility to participate (must walk 3 minutes at 0.1 MPH with handrail support), cardiopulmonary response to strenuous exertion defining exercise tolerance and safety, and allow us to pre-select testing parameters for subsequent constant velocity peak effort graded treadmill testing. Belt safety harness will be worn with a spotter behind the subject, and handrail support will be used at all times. Peak exercise tests will evaluate the cardiopulmonary response to exertion, under clinician supervision with continuous vital signs and EKG monitoring. Tests will be terminated at the subject's request, and based on American College of Sports Medicine criterion. Baseline peak test is reviewed by a cardiologist as part of our quality assurance program. The peak fitness test will be completed during Phase 1, Phase 5, and Phase 7.

Submaximal Treadmill Test: After a 12 hour fast, economy of hemiparetic gait will be measured using open circuit spirometry during a standard constant load submaximal effort treadmill walking task at a pre-established gait velocity (60-80% of self-selected floor walking velocity). This slower walking velocity is selected because untrained subjects with stroke usually cannot maintain their self-selected walking pace, precluding steady state measures of oxygen consumption that defines gait economy. The mean rate of VO₂ will be calculated based on the final 3 minutes of a 10-minute walk under steady state oxygen consumption conditions. Subjects not achieving a plateau in VO₂ will be re-tested at a lower velocity on a different date to eliminate potential confounding effects of fatigue on testing. This test will be completed before (Phase 3) and after (Phase 5) the Dietary Education (Phase 4), as well as in Phase 7 after the 6-month exercise or stretching interventions.

5. Energy Expenditure

Resting Metabolic Rate (RMR) will be measured using the ventilated hood technique while subjects lie quietly in bed for 30-45 mins under a clear plastic hood with expired air collected through a one-way valve (Weir JB deV. RMR will be measured at rest in Phase 3, 5 and 7.

Activity Monitoring: Subjects will answer activity questionnaires. They will wear an accelerometer activity monitor on their belt for 5 to 7 days to determine caloric expenditure in daily activities in Phase 5 and Phase 7.

6. Dietary Intake Assessment: A Registered Dietitian will instruct subjects on how to complete a 3-5-day food record or collect 24 hour dietary recalls that will be analyzed and used as measures of dietary habits. Dietary assessment will occur in at the beginning and end of Phase 4, as well as in Phase 7 following the 6-month interventions.

Statistical Analysis and Expected Results: Data from the study will be entered into a data set and validated by the study PI. Initially, analyses will be adjusted for site to determine whether site is a significant covariate to our outcomes of interest; however, if site is not significant, it will be dropped from further analyses. Descriptive statistics will be calculated for all variables using SAS version 9.3 (SAS Institute, Cary, N.C.) and the R statistical package. Exploratory data analyses will be performed to check the data for extreme values and to determine the distribution of values. Extreme values will be verified against original source documents. When necessary, data will be transformed to normality using appropriate transforms. A two-tailed P <0.05 will considered indicative of a significant result. In addition to P values, 95% confidence intervals will be reported. The primary variable of interest to test the main hypotheses includes: 1) total daily energy expenditure measured by RMR (indirect calorimetry) + energy expenditure during activity (accelerometry). Secondary variables include substrate oxidation measured as fat and glucose oxidation during submaximal exercise, systemic (plasma) oxidative stress, VO₂peak.

Statistical Analysis Plan

Primary Aim: To assess the effects of six months of TM+N versus ST+N on total daily energy expenditure (primary outcome) and substrate oxidation in chronic stroke survivors.

Expected Results: We anticipate that TM+N will result in significant changes in RMR and energy expenditure during activity, as well as greater reliance on fat at resting and an improved ability to switch from fat to carbohydrate utilization during submaximal exercise and after a mixed meal challenge.

Aim 2: To examine the effects of six months of TM+N versus ST+N on systemic and tissue inflammation and oxidative stress and antioxidant capacity in chronic stroke survivors.

Expected Results: We expect that TM+N will result in decreased oxidative stress in the circulation.

The change (post-pre) value of the energy expenditure and substrate oxidation outcomes, along with measures of oxidative stress and antioxidant capacity will be the dependent (outcome) variables in a series of ANOVAs (one for each outcome variable). Independent variables will include the initial value of the outcome variable, group assignment, along with the subject's age and BMI, and if needed (i.e. if there are differences between the exercise and stretching subjects) medications and medical conditions other than presence of stroke. Baseline dietary intake will be treated as covariates. These analyses will tell us if there is a differential effect of exercise versus stretch control with nutritional modification on the outcome measures.

References:

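### Sex and race are named as matching factors but are not model terms; if matching is enforced and they predict change, reported standard errors are too large

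*Combined protocol and SAP*

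**What the plan says.** In the combined protocol and SAP, the paragraph after the exclusion criteria randomises subjects 1:1 and then states: "Groups will be matched for sex and race". It gives no mechanism: no strata, blocks, minimisation or pairs. The overview under Metabolic Test by Phase and the Randomization (Phase 3) text speak only of random assignment.

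The Statistical Analysis Plan models post-minus-pre change, one model per outcome. "Independent variables will include the initial value of the outcome variable, group assignment", with age and BMI. If the arms differ, the model also takes in "medications and medical conditions other than presence of stroke". It adds: "Baseline dietary intake will be treated as covariates". The preceding section, Statistical Analysis and Expected Results, enters site at first and drops it if it is not significant. It also sets two-sided P < 0.05 and promises 95% confidence intervals. Sex and race are not model terms anywhere.

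**The concern.** A factor balanced by design should normally appear in the analysis. Balancing a prognostic factor removes its contribution from the true variance of the treatment contrast. A model that omits the factor leaves that contribution in the residual, so the reported standard error overstates the real uncertainty.

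The conditional rule cannot repair this. It names only medications and medical conditions, and it is triggered by a difference between arms, which is what matching is meant to prevent. The models cover total daily energy expenditure, substrate oxidation and oxidative stress, so the P values and intervals for all of these could be affected.

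**Working it through.** The plan gives no sample size, power, standard deviation or dropout, so there is no planned figure to reproduce. The documents supply the 1:1 allocation, two-sided 5% level, 95% intervals and model terms. R², sample size and race shares below are assumptions. R² is the share of residual change-score variance that sex and race explain beyond the planned covariates.

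**Large-sample formula, matching enforced.** Let σ² be the residual variance of the planned model and N the total sample. The model reports variance 4σ²/N for the group contrast. With both factors balanced, the true variance is 4σ²(1−R²)/N. Therefore:

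- SE ratio = 1/√(1−R²)
- type I error = 2[1 − Φ(1.960/√(1−R²))]
- power = Φ(1.960 + 0.842 − 1.960/√(1−R²)), against 80% for the model with both factors

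Example, R² = 10%: √0.90 = 0.9487 and 1/0.9487 = 1.054. The effective critical value is 1.960 × 1.054 = 2.066, so type I error is 3.9%. Power is Φ(2.802 − 2.066) = Φ(0.736) = 76.9%.

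| Assumed R² | SE ratio | Type I error | Power (80% with the terms) |
|---|---|---|---|
| 0 | 1.000 | 5.0% | 80.0% |
| 2% | 1.010 | 4.8% | 79.4% |
| 5% | 1.026 | 4.4% | 78.5% |
| 10% | 1.054 | 3.9% | 76.9% |
| 20% | 1.118 | 2.8% | 72.9% |

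**Simulation check.** N was 40 or 80 in total. Sex and race were each binary and evenly split, with R² shared equally between them. There were four other covariates, complete data and 6,000 runs per cell. Allocation was 1:1 within sex-by-race strata (enforced) or 1:1 ignoring both (not enforced). The effect was 2.802 × √(1−R²) × 2/√N. Monte Carlo standard errors are √(0.05 × 0.95/6000) = 0.3 point for type I error and √(0.75 × 0.25/6000) = 0.6 point for power.

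Results at N = 80, R² = 20%:

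| | Enforced, without terms | Enforced, with terms | Not enforced, without terms | Not enforced, with terms |
|---|---|---|---|---|
| True spread of estimate | 0.203 | 0.201 | 0.231 | 0.210 |
| Mean CI half-width | 0.456 | 0.408 | 0.456 | 0.413 |
| Type I error | 2.8% | 4.4% | 5.1% | 5.1% |
| Power | 69.3% | 77.2% | 67.4% | 75.6% |

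Under enforcement, 0.456/0.408 = 1.118, which matches the formula. The true spread barely moves, so the excess lies in the reported standard error. Without enforcement the type I error is nominal, and the loss is one of real precision (0.231 against 0.210).

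Power change from adding the terms, in points:

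| R² | Enforced, N = 40 | Enforced, N = 80 | Not enforced, N = 40 | Not enforced, N = 80 |
|---|---|---|---|---|
| 0 | −0.6 | −0.3 | −2.8 | −1.0 |
| 5% | +1.2 | +1.9 | +0.1 | +1.1 |
| 10% | +3.4 | +3.6 | +1.4 | +3.2 |
| 20% | +7.9 | +7.9 | +6.6 | +8.2 |

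**The case against.** The best defence is that the harm needs two conditions the documents do not establish. Enforcement rests on one sentence with no mechanism behind it. The outcome is also a change score already adjusted for baseline value, age, BMI and diet, which may absorb most of any sex or race effect. R² may therefore be close to zero, and the terms would then cost a little power. Conservative tests do not threaten validity. At large R² the power gain is similar with or without enforcement, so the request could be called a preference about covariates. The simulation also leaves out the site-dropping step and the conditional medication terms.

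Much of this stands. It limits the point to a conditional one, and the simulated figures do not describe the full planned procedure. It does not remove the mismatch between a stated balancing intention and models that omit the balanced factors. The covariate list is not expressly closed, but that leaves adjustment to a later choice, which prespecification would avoid.

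A reader might infer three stronger things:

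- **The omission biases the treatment effect or inflates false positives.** Randomisation is stated throughout, and the calculation points to type I error at or below 5%.
- **Matching makes the estimate itself less precise without the terms.** Its true spread is essentially the same either way; only the reported standard error is too large.
- **Individuals are paired, so a paired analysis is needed.** The text speaks of matching groups and describes no pairs.

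**Conclusion.** The point holds as a minor, cheap improvement. Sex and race are named for matching, are absent from the models, and cannot enter through the conditional rule. If matching is enforced, the reported standard error is too large by up to 2.6%, 5.4% or 11.8% at R² of 5%, 10% or 20%, so intervals are too wide and tests conservative. At R² = 0 nothing is lost.

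If matching is not enforced, the tests are not conservative. The terms are then a precision choice that pays only when R² exceeds a few percent: in the simulation they roughly broke even at 5% with N = 40.

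The mismatch is certain from the text. Its size is not, because every figure rests on assumed R², sample size and race shares, with complete data.

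**What to change.** 1. State how matching on sex and race is done.
2. Prespecify both as fixed terms in the Statistical Analysis Plan models, in the categories used for matching, and keep them regardless of significance.
3. Collapse sparse race categories by a rule set before outcome data are examined.

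This is a short SAP addition and should need no new data. The Phase 1 screening text says "Information on demographics and family medical history will be recorded", which is before Phase 3 randomisation, and matching requires both factors to be known by then.

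The cost is about 2 degrees of freedom, or a few more with several race categories. At R² = 0 with binary race, that is under about 1 point of power if matching is enforced, and roughly 1 to 3 points in small samples if it is not. A separate simulation with three race categories (assumed shares 50/40/10%, blocks of 4, 20 to 40 per arm, matching enforced, complete data) put the cost at R² = 0 at 0.2 to 1.5 points, which is the reason for the collapsing rule.

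### Randomisation (Phase 3) comes before the only pre-training accelerometry (Phase 5), so the baseline of the primary outcome is measured after allocation, with nothing in the plan to keep the allocation hidden

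*Combined protocol and SAP*

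**What the plan says.** **Outcome.** Under Statistical Analysis and Expected Results, the primary variable is "total daily energy expenditure measured by RMR (indirect calorimetry) + energy expenditure during activity (accelerometry". A TDEE value needs both parts.

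**Order of events.** Metabolic Test by Phase places randomisation after Phase 2 testing: "Volunteers then will be randomly assigned to TM+N or ST+N (control". Table 1 and the Randomization paragraph also put it in Phase 3. Phase 4 then "consists of 2 weeks of weight and dietary stabilization prior to baseline research testing", so the protocol regards Phase 5 as its research baseline. Table 1 labels Phase 5 "Metabolic Pre Testing".

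**Accelerometry.** Under Energy Expenditure, the activity monitor is worn "to determine caloric expenditure in daily activities in Phase 5 and Phase 7". The Baseline Testing (Phase 2) paragraph lists a submaximal treadmill test, a blood draw and RMR, and no accelerometry.

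**Analysis.** The dependent variable in the Statistical Analysis Plan is described as "The change (post-pre) value of the energy expenditure and substrate oxidation outcomes". On the other side of the model, "Independent variables will include the initial value of the outcome variable, group assignment", followed by age, BMI and further covariates. The plan does not say which phase supplies the pre or initial value.

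**Safeguards between Phases 3 and 6.** Dietary counselling in Phase 4 is given to everyone, and for Phase 5 the protocol says: "Subjects will be weight stabilized throughout the metabolic testing". Nothing says when participants or testing staff learn the allocation.

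**The concern.** A baseline covariate is safe in a randomised comparison because the allocation cannot have influenced it. Here the pre-training accelerometer week follows randomisation by at least the two-week diet phase. It records voluntary behaviour, which a participant who knows the allocation may change: someone expecting treadmill training might start walking more, or might rest until it begins.

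The Phase 5 value enters the model twice, in the change score and as a covariate, so a shift in one arm would pass into the estimated group effect. With no earlier accelerometry, such a shift could not be told apart from chance imbalance.

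The second route is loss. A participant who leaves between randomisation and training counts as randomised but will normally lack a pre or a post value, and so cannot enter a change-score analysis. The SAP does not say how such participants are handled.

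**Working it through.** The documents give no sample size, SD, effect size or loss rate, so there is no stated figure to reproduce. The check has three parts.

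**1. Complete TDEE values by period**

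| Period | RMR | Accelerometry | Complete TDEE |
|---|---|---|---|
| Before randomisation | at most one | none | 0 |
| After randomisation, before training (Phase 5) | yes | yes | 1 |
| After the intervention (Phase 7) | yes | yes | 1 |

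The first row says at most one because the Phase 2 paragraph puts the first RMR in Phase 2, while the RMR paragraph under Energy Expenditure puts it in Phase 3. The count of complete values is zero on either reading.

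**2. Effect of a shift in Phase 5 TDEE**

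Let d be the shift caused by knowing the allocation, in the TM+N arm relative to ST+N (signs reverse if the stretching arm shifts). Let k be the share of d still present at Phase 7, b the within-arm slope of Phase 7 on Phase 5 TDEE given the other covariates, and tau the effect of training itself.

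- Observed pre = unshifted pre + d × group.
- Post = constant + tau × group + b × (unshifted pre) + k × d × group + error.
- Substituting, (post − pre) regressed on group and observed pre has group coefficient tau + (k − b) × d.
- The total effect of assignment is tau + k × d, so the bias against it is −b × d for every k.
- The effect of training alone is tau, so the bias against it is (k − b) × d.

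With d = 10 kcal/day and b assumed to be 0.5 to 0.8:

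| Share lasting to Phase 7 | Bias against total effect | Bias against training effect |
|---|---|---|
| k = 0 | −5 to −8 | −5 to −8 |
| k = b | −5 to −8 | 0 |
| k = 1 | −5 to −8 | +5 to +2 |

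A simulation of the change-score model with k = 0 and true effect zero agreed. For a shift of 0.2 SD it gave −0.096 SD at a correlation of 0.5 (formula −0.10) and −0.16 SD at 0.8 (formula −0.16). If d = 0 this route contributes nothing.

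**3. Time at risk of loss between randomisation and training**

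One month is taken as 4.35 weeks. Phase 4 lasts 2 weeks.

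- Phase 5 of 2 weeks (Metabolic Test by Phase): 2 + 2 = 4 weeks.
- Phase 5 of 1 to 2 months (Table 1): 2 + 4.35 = 6.3 weeks, up to 2 + 8.70 = 10.7 weeks.
- The upper end does not fit the stated 9-10 months. Phases 1 to 4 take 21 + 7 + 1 + 14 = 43 days, about 1.4 months. Adding 2 months for Phase 5, 6 for Phase 6 and 1 for Phase 7 gives about 10.4 months.
- Within 10 months and with a one-month Phase 7, Phase 5 can last at most 10 − 6 − 1 − 1.4 = about 1.6 months, or 6.9 weeks. The longest consistent window is 2 + 6.9 = 8.9 weeks.

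Expected loss = 1 − (1 − m)^(weeks/4.35), with monthly loss m assumed:

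| Window | m = 1% | m = 5% |
|---|---|---|
| 4 weeks | 0.9% | 4.6% |
| 6.3 weeks | 1.5% | 7.2% |
| 8.9 weeks | 2.0% | 10.0% |

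**The case against.** The best defence is that Phase 5 is a genuine pre-training baseline. No arm-specific activity is prescribed before Phase 6, since the recommended home walking is tied to current treadmill training. Phase 4 counselling is the same in both arms and weight is controlled. Both TDEE components are recorded by instrument, which leaves testing staff little room to influence them. The aim is worded as the effect of six months of the programmes, and those six months are Phase 6, so a value taken just before training is a natural starting point. Disclosure of the allocation during Phases 4 and 5 is inferred from silence.

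Most of this stands, and it limits the point. Diet and weight control do not govern free-living activity, however, and they do not equalise losses. The silence on disclosure also cuts both ways, because nothing in the plan prevents it.

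A reader might infer that the primary result is biased, or that the treadmill effect will be understated because the shift is always subtracted. The documents support neither inference. They give no evidence of a shift or of unequal loss. Subtraction in every case also holds only against the total effect of assignment; against the training effect, a lasting positive shift in the TM+N arm (k > b) would inflate the estimate. The SAP does not say which effect is the target. Loss that is alike in both arms reduces numbers but does not by itself bias the comparison.

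The conflicting phase for the first RMR and submaximal test, and the unnamed Phase 4 food record used as the diet covariate, need reconciling. They are separate documentation matters and lend this point no weight.

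**Conclusion.** The sequence is certain: no complete value of the primary outcome exists before randomisation, and the model's pre value can only be the Phase 5 one. Confidence in that is high. Confidence that it causes material bias is low, because both routes depend on behaviour the documents do not describe.

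The sizes in the working rest on assumed values of b, d, k and m. The 1 to 10 losses per 100 randomised run from the 4-week window at 1% a month to the 8.9-week window at 5%. If the allocation changes nothing before Phase 6 and losses do not differ by arm, the bias is zero.

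This should be fixed because the exposure falls on the primary outcome and is cheap to remove, not because harm has been shown.

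**What to change.** 1. Move the one-day randomisation to after Phase 5, immediately before Phase 6. The Phase 5 value then cannot depend on the allocation, and pre-training losses fall before randomisation. Matching on sex and race is unaffected, since demographics are recorded at screening.
2. If that is not possible, withhold the allocation from participants and testing staff until Phase 5 is complete. This removes the allocation as a cause of any shift or loss, but people who leave in the window still count as randomised.
3. State in the SAP that the pre and initial value of TDEE is the Phase 5 value for both components.
4. For anyone already randomised in the present order, report losses between Phases 3 and 6 by arm. Optionally, add a sensitivity analysis of Phase 7 TDEE adjusted only for pre-allocation measures: age, BMI from the Phase 1 height and weight, and Phase 1 VO2peak. It is less precise than the baseline-adjusted analysis and cannot recover people with no Phase 7 value.

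**Cost.** A protocol amendment and a few sentences in the SAP, with no added test. Under step 1, fewer participants are counted as randomised, and the randomised population becomes those who complete the diet run-in and pre-testing. If the order changes mid-trial, the model needs an indicator of randomisation order.
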